**I. Hypotheses and Specific Aims:**

We will conduct a two site randomized clinical trial (VA Eastern Colorado Health Care System [VA ECHCS] and VA Puget Sound [PSVAHCS]) to determine whether an intervention to improve symptoms and to help Veterans adjust to living with Chronic Heart Failure (CHF), Chronic Obstructive Pulmonary Disease (COPD) and Interstitial Lung Disease (ILD) improves quality of life. The intervention will also help Veterans communicate preferences for treatment with their providers. The intervention involves routine clinical care and no experimental drugs or devices. The results will be directly relevant to Veterans who suffer with these illnesses and their families, as well as to providers, leaders in VA Central Office, and other researchers. Furthermore, this study will generate information that supports the broader dissemination and implementation of the intervention and informs the development of future palliative care and team-based interventions in the VA. Specific aims include:

**Aim 1:** Determine the effect of the intervention on (a) quality of life as a primary outcome, and (b) depression, symptom burden, advance care planning communication and documentation, disease-specific health status, emergency department visits, hospitalizations, and mortality as secondary outcomes.

**Aim 2:** Examine the implementation of the intervention.

**Aim 2a:** Assess the degree, barriers, and facilitators of implementation of various intervention components. Identify which intervention components and processes are most critical from the perspectives of patients, intervention team members, and primary care providers whose patients received the intervention.

**Aim 2b.** Evaluate the resources (e.g., personnel time and other costs) associated with the intervention, and estimate the resources needed for implementation and maintenance of the intervention in other VA settings.

The brief study title is Advancing Symptom Alleviation with Palliative Treatment (ADAPT) and will be used with participants as it provides a simple acronym.

**II. Background and Significance:**

Among Veterans, CHF and COPD are top causes of poor quality of life, hospitalizations, mortality, and health care costs. While not as common, ILD also leads to poor quality of life, has few effective treatments, and has a poor prognosis. While palliative care is effective in advanced cancer, it has not been adequately studied in CHF, ILD, or COPD. Commonalities in CHF, ILD, and COPD make them priorities for a palliative care intervention to improve quality of life in both populations. CHF and COPD commonly co-occur: there is a 20% chance a patient with COPD will have CHF, and a 30% chance a patient with heart failure will have COPD. Despite disease-specific treatments CHF, ILD, and COPD, Veterans with these illnesses still suffer from the burdens of persistent, diverse symptoms and depression that reduce quality of life. These burdens are remarkably similar in CHF, ILD, and COPD despite different organ systems and pathophysiology.

Palliative care need #1: Poor quality of life in CHF, ILD and COPD is due to similar persistent, diverse symptoms and depression. This is illustrated in the study conceptual model (**Figure 1**), which is based on Palliative care to improve quality of life in CHF and COPD\_Protocol\_v\_05.08.2018

[figure not shown]
integrating elements of Lenz' unpleasant symptom theory into an adaptation of the Wilson and Cleary model of health related quality of life. As illustrated in the conceptual model, in CHF, ILD, and COPD, the symptom experience and depression exert major influences on health-related quality of life.

1. **Symptom experience: persistent, diverse symptoms.** Patients who have CHF, ILD or COPD are burdened by the same disease-related symptoms of breathlessness (44-85%) and fatigue (66-85%) as well as pain (38-58%) and other non-disease related symptoms that reduce quality of life and persist over time. In CHF, a mean of 15 physical and emotional symptoms are experienced concurrently. Diverse symptoms reduce quality of life in patients with CHF, ILD, COPD.
2. **Depression.** Depression in CHF, ILD and COPD is a key determinant of the experience of symptoms and quality of life. Between 20-30% of patients with CHF, ILD or COPD have depressive disorders. Between 50-60% have clinically significant depressive symptoms. VA studies demonstrate that the prevalence and severity of depression in Veterans with CHF and COPD increases with disease severity.

Combining palliative symptom management with psychosocial care to reduce depression and help patients adjust to illness is an innovative approach. This approach is based on the strong correlation between depression and symptoms and evidence showing that combined treatment of depression and pain is the most effective approach for both.

Diverse symptoms and depression are not only major contributors to quality of life in Veterans, but they are also associated with numerous other adverse outcomes (Figure 1). In both HF and COPD, symptom severity and depression independently predict health care utilization (e.g., emergency department visits and hospitalizations) and mortality and contribute substantially to high care costs.

**Figure 1. Conceptual Model & Proposed Intervention Effects**

**Palliative care need #2:** Few Veterans with CHF, ILD or COPD engage in advance care planning. Advance care planning is the process of considering and communicating healthcare values and goals. An advance directive is a legal document describing preferences for future care and appointing a surrogate to make health care decisions in the event of incapacity. While the benefits of completing an advance directive are controversial, recent studies demonstrate advance care planning can reduce health care costs; increase the likelihood of dying at home and receiving care aligned with one's wishes; decrease rates of hospital admission; and increase rates of hospice admission. Advance care planning also improves patient and family satisfaction and reduces stress, anxiety, and depression in surviving relatives. Despite these benefits and professional heart and lung organization recommendations, few Veterans with CHF, ILD or COPD engage in advance care planning. In addition, patients with CHF, ILD and COPD are often hospitalized at the end of life, although many say they would prefer to die at home.

**By addressing diverse symptoms and depression to improve quality of life, and implementing a successful advance care planning intervention, this study will overcome limitations of prior studies**

Despite disease-specific care in CHF, ILD, and COPD, patients experience poor quality of life. Disease management interventions in either illness have not consistently improved quality of life because they have not simultaneously addressed diverse symptoms and depression (Figure 1). In COPD, intensive pulmonary rehabilitation improves quality of life, but has limited reach as most veterans cannot access or receive pulmonary rehabilitation.

Prior palliative care interventions to improve quality of life in CHF, ILD, or COPD are sparse, have mixed results, and did not use high quality randomized study designs. Furthermore, these studies did not evaluate advance care planning outcomes, a key component of palliative care. In the most promising study, common symptoms including depression and pain did not improve because providers often did not follow the palliative care consult recommendations. By using a collaborative care model that integrates palliative care into primary care, our intervention will address this barrier.

By complementing disease-specific care with the addition of palliative and psychosocial care to address diverse symptoms and depression simultaneously, we hypothesize the proposed intervention will succeed in improving quality of life. In addition, the intervention will implement an advance care planning intervention that successfully improved advance care planning communication in COPD (see Preliminary Studies). Because both CHF, ILD and COPD have common barriers to advance care planning, our advance care planning intervention is likely to succeed.

**Limitations of palliative care delivery models will be addressed in this proposal to increase the reach and potential for dissemination of palliative care**

1. Need to integrate palliative care into primary care. The predominant care delivery model in palliative care is inpatient, consultative care focused on the end of life. However, both patients with CHF and providers believe palliative care should be provided earlier in CHF and integrated into chronic outpatient care. Most of the care of Veterans with CHF or COPD takes place in primary care, and both primary care providers (PCPs) and specialists believe palliative care should be provided through primary care. The intervention integrates palliative care into primary care through (1) a nurse who provides palliative care and collaborates with the Veteran's PCP, and (2) once a palliative care plan is approved by the PCP, palliative care orders are written for the PCP to review and sign
2. Specialist, consultative model of palliative care cannot be scaled-up to CHF and COPD. Given the difficulty assessing when end of life is near and talking to patients about palliative care, as well as concerns about professional control, providers avoid referring patients for palliative care. Furthermore, there is an inadequate palliative care workforce to provide care for the large numbers of Veterans with advanced CHF or COPD. Patients with advanced CHF prefer not to see additional providers for their care, including palliative care specialists. Rather than using a consultative model, the study uses population-based identification of patients. A nurse and social worker are trained to provide basic palliative care and are supervised by a palliative care specialist.
3. Prior palliative care interventions are not structured and thus are difficult to replicate or disseminate. The proposed palliative care intervention is structured and operationalized in a treatment manual which will facilitate replication and dissemination.

**Study innovation and rationale for Aim 2: within the context of an effectiveness trial, examine implementation issues**

Blending the efficacy and effectiveness stages of intervention testing can (1) reduce the time delay between the discovery of health care innovations and their implementation; (2) produce additional knowledge for researchers; and (3) increase the operations and policy relevance of clinical research. VA researchers have emphasized the importance of understanding challenges to implementation early in intervention studies. In the context of an effectiveness trial, VA QUERI has recommended blending by testing the effects of a clinical intervention while simultaneously observing and gathering information on implementation. QUERI has termed this a "hybrid effectiveness-implementation" (type 1) study design.

The proposed study is innovative in that it is a “pragmatic” or “practical” (i.e., “effectiveness”) clinical trial that uses a type 1 hybrid design to generate information on implementation of team-based and palliative care interventions. It is an effectiveness trial because (1) population-based sampling is used to identify a “real world” population of veterans; (2) the intervention “dose” is allowed to vary with Veteran needs as would occur in the clinical setting; and (3) the analysis includes all patients regardless of compliance with the intervention and missing data. As a type 1 hybrid, the study will include collection of data on valuable intervention content and processes from the perspectives of patients, intervention team members, and PCPs whose patients received the intervention (**Aim 2a**). This data will yield information about barriers and facilitators of intervention delivery that will be important to plan subsequent implementation if the intervention is successful. If the intervention is not successful, this aim will inform subsequent implementation of other team-based, palliative care, or specialty/primary care interventions.

The operational partners contributing to this study recommended we determine the personnel time and other costs to implement and maintain the intervention (**Aim 2b**). This information, combined with an understanding of whether the intervention improves quality of life or advance care planning outcomes, was most important to them in considering intervention implementation and dissemination.

Research staff at VA ECHCS will assist PSVAHCS in some aspects of recruitment, follow-up data collection and the process evaluation. The Intervention SW and RN at each site will interact with participants at both sites.

### **III. Preliminary Studies:**

Preliminary studies demonstrate study and intervention feasibility and likelihood of success:

- 1) The Principal Investigator (PI, [name]) developed and conducted initial pilot-testing of the CASA palliative symptom management component, which includes evaluations and treatments for fatigue, breathlessness, and pain, as Director of outpatient CHF palliative care programs at the University of Colorado Hospital (published sample of patients) and the Denver VAMC.
- 2) The psychosocial care component of the intervention was developed by [name] (see letter of support) through grants from the NIMH (R34MH73566) and the American Heart Association (AHA 0555699Z). In a randomized pilot study of the intervention (n=37), the mean Beck Depression Inventory-II (BDI-II, scale range 0-63) scores for the intervention patients improved from 21.1 to 11.8, while those in the usual care remained approximately the same, 17.8 to 16.2 (mixed effects model, treatment assignment by time interaction  $F=5.45$ ,  $p=0.009$ ). Defining treatment response as a 50% or greater decline in BDI-II score, 9/19 (47%) responded in the intervention group as compared with 1/18 (5.5%) in the usual care group.
- 3) In a single arm pilot study of 15 patients with advanced stage (GOLD III/IV) COPD, depression (Patient Health Questionnaire-9), anxiety (Generalized Anxiety Disorder-7), and overall quality of life (St. George Respiratory Questionnaire) improved with CASA over three months (effect sizes of 0.64, 0.54, and 0.22 respectively). The nurse was able to continue the intervention after the study concluded, and 10 patients (67%) elected to continue the intervention.
- 4) In a single arm pilot study of 17 patients with CHF (15 Veterans at the Denver VAMC), 16 completed the study, and symptom distress, depression, anxiety, and quality of life improved with CASA over three months (using the same measures as in the proposed IIR study, effect sizes of 0.64, 0.12, 0.57, and 0.27 respectively). This study was funded by VA QUERI RRP 11-239 (PI: [name]). As planned in the intervention protocol, the CASA intervention team met weekly, and the nurse and social worker each provided a mean of 6 phone visits per patient.
- 5) In a RCT of 376 Veterans with COPD conducted by Co-I [name] (VA HSR&D IIR 02-292), advance care planning communication increased from 11% to 30% using the patient-completed preference form.

## IV. Research Methods

### A. Outcome Measure(s):

**Aim 1:** The measures were chosen to reflect domains of the conceptual model (Figure 1) as follows (instrument abbreviations defined below):

- **Antecedents:** Demographics; CHF factors (e.g., left ventricular ejection fraction); COPD factors (e.g., spirometry)
- **Symptom Experience:** GSDS (symptom distress), Symptom assessments
- **Depression:** PHQ
- **Health-Related Quality of Life:** FACT-G (primary outcome measure), QUAL-E, KCCQ-12, CCQ, K-BILD
- **Health Care Utilization:** Hospitalizations
- **Advance care planning communication, documentation:** patient-reported advance care planning communication, advance directive documentation in Electronic medical record review

1. **FACT-G** (primary outcome): The Function Assessment of Chronic Illness Therapy-General is a widely used, valid, reliable (alpha range, 0.88-0.92), and responsive 27 item self-report measure of health-related quality of life that includes domains of physical, social/family, emotional, and functional well-being. Norms for the general population allow FACT-G scores to be measured and compared across study populations. Validity in CHF and COPD has been demonstrated through FACT-G correlations with disease severity.

2. **QUAL-E:** The Quality of Life at the End of Life is a valid and reliable self-report measure of several domains, each scored separately, of quality of life in advanced illness.

3. **GSDS:** The General Symptom Distress Scale is a single item measure of overall symptom distress that is reliable and valid and asks, "In general, how distressing are all of your symptoms to you?" It is rated on 0 ("not at all distressing") to 10 ("extremely distressing") on a numeric rating scale.

4. **PHQ-8:** The Patient Health Questionnaire-8 is an 8-item valid and reliable instrument that provides a continuous measure of depressive symptoms and is sensitive and specific for a diagnosis of major depressive disorder.

5. **GAD-7:** The Generalized Anxiety Disorder-7 is an 7-item valid and reliable screening instrument for four common anxiety disorders in primary care (post-traumatic stress disorder, generalized anxiety disorder, panic disorder, and social anxiety disorder). It provides a continuous measure of anxiety symptoms.

6. **PEG:** The PEG is a reliable and valid 3-item scale of pain intensity and interference. Patients rate the pain's intensity and interferences with their enjoyment of life and general activity on a numeric rating scale ranging from 0 ("no pain" or "does not interfere") to 10 ("pain as bad as you can imagine" or "completely interferes").

7. **PROMIS Fatigue:** The Patient Reported Outcomes Measurement Information System (PROMIS) Fatigue Scale is a 4-item scale that measures fatigue impact and fatigue experience. Patients rate how much fatigue they have experienced and how much fatigue has bothered them on a 5-point Likert-type scale ranging from 0 ("not at all") to 5 ("very much").

8. **ISI:** The Insomnia Severity Index is a 7 item reliable and valid instrument to quantify perceived insomnia severity.

9. **Constipation and Numbness/Tingling:** These symptoms will each be assessed by one question asking how much the symptom distressed or bothered the respondent in the last week using a 6 point Likert-type scale from no symptom to very bothersome.

10. **KCCQ-12:** The Kansas City Cardiomyopathy Questionnaire is a 12-item self-administered validated questionnaire (administration time 5-10 minutes) that measures CHF-specific health status. It is a shortened version of the KCCQ 23 item measure which is reliable, sensitive to clinical change, and predicts hospitalization and mortality. Additionally, we will ask two questions assessing how bothersome symptoms are. It will be administered to Veterans with CHF.

11. **CCQ:** The Clinical COPD Questionnaire is a self-administered 10-item measure of COPD symptoms, functioning, and emotional well-being. It is well-validated, reliable, and responsive. It will be administered to Veterans with COPD.

12. K-BILD: The King's Brief Interstitial Lung Disease is a 15-item self-completed health status measure for ILD. It is validated and can be used to assess ILD from the patient's perspective. It will be administered to Veterans with ILD.

12. Demographics/Study Form: Age, gender, race and ethnicity, education level, and clinical variables will be determined at the enrollment visit from the electronic medical record and patient self-report. For example, spirometry results (COPD), NYHA classification (CHF), etiology of CHF or COPD, most recent ejection fraction (CHF), and BNP or NT-pro BNP (CHF) will be documented. Medical history (including comorbidities), current medications, number of hospitalizations in the previous year will also be collected at the time of the enrollment visit. Patients' current care, including palliative care, mental health, cardiology, pulmonology, hospice and specialist pain care will be ascertained at baseline and 6 months. At the 6 and 12 month study visit, patients will be asked to relate interim events, including hospitalizations, the reasons for them, and for permission to obtain medical records relevant to such events from VA and non-VA facilities. Medications from the medical record will be documented again at the six month visit.

13. Advance care planning communication will be measured using patient report questions at the baseline and 6 month study visits. Advance directive documentation will be defined by the presence of any of the following notes in the electronic medical record at baseline and 6 months: advance directive discussion; scanned advance directive (either a living will or durable power of attorney for health care); or medical orders for life-sustaining treatment.

14. Hospitalizations/emergency room visits, mortality and risk of hospitalization and/or death: The following events will be assessed during the study period through VA and non-VA facility medical record review to supplement patient report: hospitalization (with cause) and mortality. We will also review medical records for intensive care use and end of life care patterns. We will also assess risk of hospitalization and/or death for participants during the study. Vital status will also be ascertained via the VA Vital Status File and the National Death Index.

15. Telephone Interview for Cognitive Status (TICS): The Telephone Interview for Cognitive Status is an 11-item verbally administered test of cognitive status. The TICS takes approximately 4 minutes to administer and assesses memory and other cognitive functions. The TICS was originally developed to discriminate between cognitive normals and dementia patients and has demonstrated good sensitivity and specificity when discriminating between normals and individuals with mild cognitive impairment. The TICS will be used as a covariate in the analyses.

16. Satisfaction surveys: Satisfaction with health care and the study will be assessed. Questions were adapted from the CANHELP Questionnaire.

**Aim 2a:** We will conduct a mixed method (i.e., combination of quantitative and qualitative) evaluation to assess intervention implementation.

Intervention database: The intervention database will be used to track intervention content and processes.

Brief patient interviews: After the 6 month outcome measurement, we will conduct interviews with Veterans randomized to the intervention arm to ask for their feedback on the intervention.

Intervention Close Out Summary: The intervention team will complete an Intervention Team Intervention Close Out Summary on each Veteran once they complete the intervention.

Focused Group Discussion with Intervention Team: We will conduct structured group discussions with intervention team members at the completion of the project intervention period to debrief about how the intervention was implemented.

Surveys of PCPs: We will administer a brief survey to all PCPs who have patients who have completed the intervention.

**Aim 2b:** We will evaluate the resources and costs to implement and maintain the intervention. Data for the *costs to implement* (i.e., start-up costs) and the *cost to maintain* the intervention will be collected separately. At a minimum, the costs to implement will include personnel training, database development; the costs to maintain will include identification of eligible Veterans and personnel time to provide the intervention (e.g., patient visits/phone calls; team meetings; communication/coordination with PCPs).

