**Table 4. Intervention Overview**

Intervention Component	Personnel
Algorithm-guided symptom management: breathlessness, fatigue, pain, trouble sleeping	Registered Nurse (RN)
Structured psychosocial care, targeting depression and adjustment to illness; advance care planning	Social Worker
Team collaborative care model: 30-60 minute weekly team meetings	RN, LCSW, palliative and primary care providers

with CHF, ILD, or COPD and to activate/empower them to discuss issues related to their illness with their care providers. The counseling will be supplemented with antidepressant medication if the Team agrees providing antidepressant medication is an appropriate, evidenced-based recommendation. The social worker will also follow up on the patient-completed advance care planning preference form to help patients clarify health care goals and complete written advance directives. The nurse will assist the social worker as needed for this part of the intervention.

**Advance Care Planning:** The intervention team will meet with the patient one time to discuss care goals. Using a structured guideline, participants understanding of their illness will be assessed. Questions about what is important, goals, concerns and fears will be asked. If a caregiver is present, s/he will be invited to participate in the discussion. The discussion will be documented in the medical record.

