**Control Group (treatment as usual plus information from baseline surveys and self-care materials)**

Patients in the control group will continue to receive care at the discretion of their providers, which may include referrals to and ongoing care from cardiology, pulmonary, palliative care, or mental health. They will also have the same amount of interaction with research assistants as the intervention patients, completing questionnaires and participating in study visits at the same frequency. Patients' providers will be given the results of all baseline depression surveys if screen positive for depression. For example, patients in the usual care arm who have significant depressive symptoms will be notified of this and their providers will also be contacted. Referring providers will then assume responsibility for depression care at their discretion, with no constraints on treatment or referrals. Therefore, the usual care patients may benefit from self-care materials or the feedback of screening instruments to their referring providers. This sets a high but appropriate standard by which to judge the effectiveness of the intervention. We considered a control group that included time with a nurse or social worker to match the intervention patients' time ("attention control"). However, this is not feasible as the intervention "dose" of nursing and social work care varies according to patient needs and symptoms. It would not be possible to match the "dose" of provider time in both groups.

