**D. Description, Risks and Justification of Procedures and Data Collection Tools:**

**Aim 1:** Study personnel will administer measures four times: enrollment (baseline), 4 months, 6 months and 12 months (**Table 5**). The baseline and 6-month measures which are comprised of approximately 120 questions and are expected to last 45 minutes, will be obtained during an in-person visit, by mail and phone or by video teleconference. We will allow patients to complete 4 month and 12 month measures by mail or phone if they prefer. Veterans will be offered an incentive for completing each of the 4 study visits (\$10 at baseline, \$10 at 4 months, \$15 at 6 months, \$10 at 12 months). Patient reported survey data is necessary to achieve study aims as the primary outcome is quality of life which is patient perceived. Demographic data and information from medical record review is necessary to determine secondary outcomes. We have implemented the following protections:

Table 5. Study Visits and Assessments	Baseline	Month 4	Month 6	Month 12
Demographics/study form	X			
FACT-G (primary outcome)	X	X	X	X
PHQ-8, GAD-7	X	X	X	
KCCQ-12, CCQ, K-BILD	X	X	X	
QUAL-E, Symptom Assessment, GSDS	X		X	
Advance care planning communication, assess for advance directive documentation	X		X	
Medications	X		X	
Health care utilization, vital status, risk of hospitalization/death			X	X
Use of other medical services	X		X	

Satisfaction	X	X
--------------	---	---

Medical record data will be gathered for up to ten years after each participant concludes active study participation. The purpose of this is to determine the effect of the intervention on long-term health and health care use. This could include but is not limited to hospital discharge summaries, progress notes, operative notes, laboratory results, and diagnostic tests.

Protection against loss of confidentiality.

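### The advance directive documentation outcome may be met by the intervention team's own discussion note, and the plan neither settles whether that note counts nor reports the components separately

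*Protocol*

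**What the plan says.** Aim 1 of the protocol (Section I) lists among its secondary outcomes "depression, symptom burden, advance care planning communication and documentation, disease-specific health status, emergency department visits, hospitalizations, and mortality as secondary outcomes". Item 13 of Section IV.A defines the documentation part: "Advance directive documentation will be defined by the presence of any of the following notes in the electronic medical record at baseline and 6 months". The qualifying items are "advance directive discussion; scanned advance directive (either a living will or durable power of attorney for health care); or medical orders for life-sustaining treatment". One item is enough, and no rule is given on note title, content or author.

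The Advance Care Planning paragraph of the Description of the Intervention states: "The intervention team will meet with the patient one time to discuss care goals". It closes with: "The discussion will be documented in the medical record". In the same section, the social worker follows up on the preference form "to help patients clarify health care goals and complete written advance directives".

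For the other arm, the Control Group section says: "Patients in the control group will continue to receive care at the discretion of their providers". It schedules no care-goals discussion and requires no note.

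Table 5 has a row labelled "Advance care planning communication, assess for advance directive documentation", marked at baseline and month 6. Both the protocol (Section F) and the SAP treat documentation as one binary outcome in a logit mixed model. Neither plans an analysis by component or by note author, and the SAP does not repeat or refine the definition.

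**The concern.** One of the three ways to meet the outcome resembles something the intervention team is instructed to do and to chart. If the team's care-goals note is abstracted as a discussion note, an intervention patient can become a success simply because the visit took place. A control patient can succeed only through usual clinicians. For that component the outcome would then partly measure delivery of the intervention.

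What is at stake is interpretation. Section II of the protocol reports that the operational partners most wanted resource information combined with knowing whether quality of life or advance care planning outcomes improve. A single composite percentage per arm would not tell them whether more Veterans had a directive or treatment orders on file, or whether the trial's own charting made the difference. The protocol's background itself separates talking about values and goals from the legal document called an advance directive, and the composite merges the two.

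**Working it through.** **The plan's own figure.** The only power statement concerns FACT-G: 115 completers per arm, a difference of 6 points with SD 15 (d = 0.4), two-sided alpha 0.05. The normal approximation gives 85.8%, against 85% stated, so it reproduces. It says nothing about documentation, for which the plan gives no power figure or expected rate.

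**Inputs for the illustration**
- From the protocol: 400 patients randomised 1:1, so 200 per arm.
- Assumed, because the documents give no figure: the proportion p0 documented without any team note, equal in both arms, at 10% to 60%. Notes already present at baseline count under the definition, so a high p0 is possible.
- Assumed: the share f of intervention patients, independent of p0, who have a team note that is counted. If the team's note is not counted, f = 0.
- Assumed: no effect on scanned directives, orders or usual clinicians' notes.

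**Timing.** About six visits per discipline at two a month is 6/2 = 3 months, so the team's note could well be in the record by the month 6 review.

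**Formulas.** Intervention rate p1 = p0 + (1 − p0)f, so the difference is (1 − p0)f. Power is that of a two-sided comparison of two proportions at 0.05, Φ[(difference − 1.96·SE0)/SE1], with SE0 from the pooled rate and SE1 from the separate rates. This approximates the planned logit mixed model.

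**Example, p0 = 30%, f = 25%.** p1 = 0.30 + 0.70 × 0.25 = 0.475, a difference of 17.5 points. The pooled rate is 0.3875. SE0 = √(0.3875 × 0.6125 × 2/200) = 0.0487. SE1 = √((0.30 × 0.70 + 0.475 × 0.525)/200) = 0.0479. Power = Φ[(0.175 − 1.96 × 0.0487)/0.0479] = Φ(1.66) = 95%.

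**Results, 200 per arm**

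| p0 | Difference at f = 0 | Difference (power) at f = 25% | Difference at f = 75% | Smallest f for 80% power |
|---|---|---|---|---|
| 10% | 0 | 22.5 points (about 100%) | 67.5 points | 11% |
| 30% | 0 | 17.5 points (95%) | 52.5 points | 19% |
| 50% | 0 | 12.5 points (71%) | 37.5 points | 28% |
| 60% | 0 | 10 points (56%) | 30 points | 33% |

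At f = 75%, power is about 100% in every row. With 150 per arm instead of 200, the smallest f runs from 13% to 38% as p0 goes from 10% to 60%; with 115 per arm, from 15% to 43%.

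An analysis that leaves out the team's notes has an expected difference of 0 in every row, by construction.

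**The case against.** The strongest objection is that the decisive link is missing from the documents. Item 13 counts a note of a discussion about advance directives. The intervention paragraph describes a conversation about illness understanding, goals, concerns and fears. Nowhere is it said that this conversation is filed or abstracted under the counted note type. This stands, and it is why the lower bound is zero. It also shows the gap: the definition leaves the question to the abstractor.

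Second, more documentation is an intended effect in a pragmatic trial, and the contrast with usual care is the treatment contrast. That also stands. A reader might infer that the comparison is biased, or that the endpoint is merely a fidelity measure. The documents do not support either. Randomisation is intact, and the social worker's help with written directives gives a route to real differences in completed documents.

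Third, a reader might want to redefine the outcome so that team-written notes never count. That is hard to defend as the main definition. Directives completed with the social worker's help are also products of the intervention, so dropping only the team's notes draws a debatable line. A usual clinician who sees a charted discussion may also not repeat it, and the stricter outcome would then understate the effect.

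Fourth, the information is partly within reach. The abstraction must already look for distinct note types, the Aim 2a database records visit content, and communication is a separate patient-reported outcome. This is true, but no analysis by component or author is planned, so nothing commits the trial to reporting it.

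**Conclusion.** The point holds in a limited form. The definition lets a discussion note alone meet the outcome, the intervention includes a charted care-goals discussion, and the plan does not say whether that note counts. If it counts, an arm difference could arise partly or wholly from delivery of the intervention.

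The size cannot be fixed from the documents. It is 0 if the note is not counted. If it is counted for a quarter of intervention patients, it is 10 to 22.5 points over assumed control rates of 60% down to 10%. If it is counted for three quarters, it is 30 to 67.5 points. With 200 per arm, a counted note in about 11% to 33% of intervention patients would be enough for 80% power with directives and orders unchanged. A reader might infer that a large artefact is certain; that would require both a high share of counted notes and a low control rate, and the documents give neither figure.

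This concerns one element of the secondary outcomes. The primary outcome and patient-reported communication do not depend on it. It is an inexpensive improvement to the plan and does not threaten the trial's main conclusion.

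**What to change.** Keep the composite as defined, and make four additions:

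1. State in protocol Section IV.A, item 13, and in the SAP, whether the team's care-goals note counts as a qualifying discussion note.
2. Record note type and note author in the chart abstraction already planned.
3. Report the three components separately by arm: scanned directive, orders for life-sustaining treatment, and discussion note.
4. Pre-specify a sensitivity analysis that excludes discussion notes written by the study team.

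The cost is two abstraction fields and a few lines of text. The sensitivity analysis may understate the effect where usual clinicians do not repeat a discussion the team has already charted, so it should be read beside the composite and not in place of it.
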